
APPENDIX A: Schedule of Treatment and Evaluations

	Screening -28 Days	Cycle 1	Cycle 2	Cycle 3	Cycle 4	Cycle 5	Cycle 6	Cycle 7	Cycle 8 (repeat until off drug)	Day 15 (± 1 day) each Cycle	End of Treatment ¹⁴	Every 12 weeks ¹³	Follow Up ¹²
Signed ICF	X												
Review inclusion/exclusion	X	X											
Medical history ¹	X												
Physical examination	X	X	X	X	X	X	X	X	X		X	X	
Height (cm)	X	X ²											
Weight (kg)	X	X	X	X	X	X	X	X	X				
BSA calculation ²		X	X	X	X	X	X	X	X				
Vital signs ³	X	X	X	X	X	X	X	X	X		X	X	
ECOG PS	X	X	X	X	X	X	X	X	X		X		
CT/ MRI scan / tumor measurements ⁴	X ^{8a}			X ⁸		X ⁸		X ⁸			X ^{8, 10}	X ⁸	
ECG ¹⁸	X	X	X	X	X	X	X	X	X ¹⁸		X ¹¹	X ¹¹	
ECHO (with ejection fraction) ¹⁹	X		X		X		X		X ¹⁹		X ²²	X	
CBC w/differential & plts ^{5, 20}	X	X ¹⁶	X	X	X	X	X	X	X	X	X ¹¹	X ²¹	
Serum chemistries ^{6, 20}	X*	X ¹⁶	X	X	X	X	X	X	X	X	X ¹¹		
Urinalysis ⁷	X										X ¹¹		
Serum/urine pregnancy test	X												
Randomization		X ¹⁵											
Aldoxorubicin administration ¹⁷		X	X	X	X	X	X	X	X				
Topotecan		X	X	X	X	X	X	X	X				
Concomitant medications	X ⁹	X	X	X	X	X	X	X	X		X		
Adverse events		X	X	X	X	X	X	X	X		X		
Telephone follow-up													X

NOTE: All assessments must be performed within 72 hours of each specified time parameter, except Cycle 1 (see Section 6 for details).

*Arterial blood gas test, if needed, to confirm acid levels.

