
Study Design and Methodology:
 
This is a phase 2b open-label study evaluating the efficacy and safety of aldoxorubicin administered at 230 mg/m² (170 mg/m² doxorubicin equivalent) intravenously on Day 1 every 21 days compared to topotecan administered either IV at doses of 1.5 mg/m²/day for 5 consecutive days starting on Day 1, and repeated every 21 days, or 4 mg/m² administered as a 30 min IV infusion on Days 1, 8 and 15 every 28 days. Subjects will be randomized 1:1 to receive either aldoxorubicin or topotecan. Treatment with granulocyte colony-stimulating factor (G-CSF) should be administered to all subjects as per investigator's clinical judgment or according to ASCO Guidelines (Appendix E).^[31] Note: aldoxorubicin, at higher doses, has been associated with >20% incidence of grade 3 or 4 neutropenia.
 
Subjects will visit the study site on Day 1 of each cycle. Safety monitoring, including AEs, a directed physical examination, laboratory evaluations (serum chemistry and complete blood count [CBC]), vital signs, weight measurements, Eastern Cooperative Group performance status (ECOG PS) and ECGs will be performed on Day 1 of each cycle (for all subjects). Subjects receiving aldoxorubicin will have blood drawn for serum electrolytes to evaluate the anion gap prior to each drug administration. They will have CBCs and serum chemistries on Day 15 (\pm 1 day) of each cycle as well. Cardiac function will also be followed periodically (per schedule of evaluations) with ECHO for subjects receiving aldoxorubicin. Treatment will continue until tumor progression is observed, subject asks to withdraw, or unacceptable toxicity occurs.
 
Tumor response will be monitored at baseline, every 6 weeks (\pm 5 days) from Cycle 1-Day 1 through week 36, and then every 12 weeks (\pm 5 days) until disease progression using the Response Evaluation Criteria in Solid Tumors (RECIST) 1.1 criteria.^[22] Overall survival, PFS, and PFS at 4 and 6 months will be evaluated. Objective response rate (ORR; complete response [CR] and partial response [PR]), disease control rate (ORR plus stable disease [SD] at 4 months) and quality of life (ECOG PS) will be assessed.
	

Name of Sponsor/Company: CytRx Corporation	
Protocol Number: ALDOXORUBICIN-P2-SCLC-01	Phase of Development: 2b
Study Population and Main Criteria for Inclusion/Exclusion:	
Inclusion Criteria:	
Subjects must meet the following criteria to be included in the study:	

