
Test Product and Mode of Administration: Aldoxorubicin: Lyophilized powder in vials that contain 200 mg of aldoxorubicin reconstituted by adding a solution of 50% ethanol: 50% sterile water, administration completed within 2 hours (of being reconstituted) as an approximate 30 minute IV infusion in Lactated Ringer's solution. Total dose of 230 mg/m² (170 mg/m² doxorubicin equivalent).
 
Topotecan: Topotecan for Injection is supplied as a sterile lyophilized, buffered, light yellow to greenish powder available in single-dose vials. Each vial contains topotecan hydrochloride equivalent to 4 mg of topotecan as free base. The reconstituted solution ranges in color from yellow to yellow-green and is intended for administration by intravenous infusion (IVI). Each topotecan 4-mg vial is reconstituted with 4 mL Sterile Water for Injection. Then the appropriate volume of the reconstituted solution is diluted in either 0.9% Sodium Chloride IVI or 5% Dextrose IVI prior to administration. Because the lyophilized dosage form contains no antibacterial preservative, the reconstituted product should be used immediately.
	

Criteria for Evaluation: Efficacy: The following efficacy variables will be evaluated as noted:
 
 • PFS • PFS at 4 and 6 months • OS • Objective tumor response (RECIST 1.1 criteria)^[22] • Disease control rate (ORR + SD at 4 months) • Investigator assessment as measured by ECOG PS 	

Name of Sponsor/Company: CytRx Corporation	
Protocol Number: ALDOXORUBICIN-P2-SCLC-01	Phase of Development: 2b

Safety: The following safety variables will be assessed over the duration of the study:
 
 • AEs • Ability to remain on assigned treatment (tolerability) • Clinical and laboratory data including physical examinations, vital signs, weight, ECHO evaluations, ECG results and laboratory test results • Use of concomitant medications 	

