
Statistical Methods: In accordance with the intention-to-treat principle, all randomized subjects will be evaluated for efficacy. All subjects who receive at least 1 dose of study medication will be evaluated for safety.
 
Efficacy: The primary analysis of PFS will be carried out when 110 PFS events have occurred, approximately 6 months following the completion of enrollment of 132 subjects. Survival distributions will be estimated using the Kaplan-Meier method and the 2 groups will be compared using a two-sided, unstratified log rank test at the $\alpha=0.05$ level of significance.
 
Tumor response will be monitored at baseline, every 6 weeks (± 5 days) from Cycle 1-Day 1 through week 36, and then every 12 weeks (± 5 days) until disease progression. The percentage of subjects with CR or PR, or SD will be evaluated and the disease control rate (CR, PR and SD at 4 months) will be compared using Pearson's chi-square test, or if 20% or more of the expected cell frequencies are less than 5, Fisher's exact test. Investigator reported outcomes as assessed by the ECOG PS will be analyzed using analysis of covariance.
 
Subjects in each group will be stratified according to their initial PS (ECOG PS 0-1 vs 2) and whether they had progressed in less than or greater than 90 days after their initial chemotherapy.
 
Sample Size Justification: Power calculations and subject numbers were calculated based on the primary endpoint of PFS. Reviewing the literature for studies that have evaluated topotecan as treatment for patients that have relapsed or not responded to first line therapies, it is estimated that the median PFS for the topotecan group will be 3.5 months and that the median PFS for the aldorubicin group will be 6.5 months. Based on the use of a two-sided log rank test at the $\alpha=0.05$ level of significance, a total of 110 PFS events will be required for 90% power to detect this difference. Assuming an 18 month accrual period and a 6 month follow-up period after enrollment of the last subject, approximately 132 subjects will be needed to achieve the total of 110 PFS events.
 
Safety: The safety data will be summarized by treatment group. The treatment groups will be compared with respect to occurrence of each AE. Total number of AEs leading to withdrawal, and abnormal laboratory tests will be compared between groups using Fisher's exact test. Adverse events, ability to remain on assigned treatment (tolerability), and abnormal findings on physical examinations, vital signs, weight, ECG results, laboratory test results, and use of concomitant medications, will be assessed to characterize the safety profile of the treatment regimens. Descriptive statistics denoting the changes from baseline to the final assessment visit with respect to key laboratory parameters and vital signs will also be provided.
	

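### The Amendment 3 Appendix A grid shows no tumor scan at weeks 24, 30 and 36, which the synopsis text requires, and it counts scans in cycles where the text counts calendar weeks

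*Combined protocol and SAP*

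**What the plan says.** The scan rule appears twice in the Amendment 3 synopsis, under Study Design and Methodology and under Statistical Methods (Efficacy). Assessment is 6-weekly, with a 5-day window either side, "from Cycle 1-Day 1 through week 36, and then every 12 weeks" until progression. The clock is calendar time and no arm is treated differently.

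In Amendment 3 Appendix A, the row "CT/ MRI scan / tumor measurements ⁴" has marks at Screening, Cycles 3, 5 and 7, End of Treatment and Every 12 weeks. The column "Cycle 8 (repeat until off drug" is blank in that row, whereas the ECG and ECHO rows carry footnoted marks there. The post-baseline scan marks refer to footnote 8, the row label to footnote 4 and the Every 12 weeks column to footnote 13. The text of these footnotes is not in the supplied document.

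Cycle length depends on the regimen. Aldoxorubicin is given "intravenously on Day 1 every 21 days compared to topotecan". Topotecan is given either "for 5 consecutive days starting on Day 1, and repeated every 21 days" or as a "30 min IV infusion on Days 1, 8 and 15 every 28 days".

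Criteria for Evaluation lists "PFS at 4 and 6 months" as an efficacy variable beside PFS, the primary endpoint.

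**The concern.** Sites often schedule scans from the grid. Read alone, it shows nothing for weeks 24, 30 and 36, so a site could go from Cycle 7 to the 12-weekly column. Two things are then at stake. The 6-month PFS rate falls at about week 26 and relies on the week-24 scan. The dating of progression, which defines the primary endpoint, could also differ between sites that follow the grid and sites that follow the text. A grid tied to cycles adds a further problem: subjects on 28-day topotecan would be scanned on a different clock from the aldoxorubicin arm.

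**Working it through.** **The plan's own figure.** Hazard ratio = 3.5/6.5 = 0.538. Events = 4 × (1.960 + 1.282)² / (ln 0.538)² = 109.7, so 110, as stated. With exponential PFS, 18 months of uniform accrual and 6 months of follow-up, 132 subjects give 66 × (0.917 + 0.766) = 111.0 events. The scan question changes neither figure.

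**Scan weeks.** Week = (cycle − 1) × cycle length / 7.

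| Schedule | Scan weeks up to 6 months (week 26.1) |
|---|---|
| Text | 6, 12, 18, 24 |
| Grid, 21-day cycles (Cycles 3, 5, 7) | 6, 12, 18 |
| Grid, 28-day cycles (Cycles 3, 5, 7) | 8, 16, 24 |

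In 21-day cycles, weeks 24, 30 and 36 are Day 1 of Cycles 9, 11 and 13, all inside the unmarked column. The documents do not say when the 12-week interval starts. Counted from week 18, the next scan is week 30; counted from week 36, it is week 48. Both come after 6 months.

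**6-month PFS.** Assume exponential PFS at the plan's medians, with 1 month = 4.35 weeks: S(w) = 0.5^(w / (4.35 × median)).

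| | Aldoxorubicin (6.5 months) | Topotecan (3.5 months) | Difference |
|---|---|---|---|
| True, 6 months | 52.7% | 30.5% | 22.2 |
| Last scan week 24 | 55.5% | 33.5% | 22.0 |
| Last scan week 18 | 64.3% | 44.1% | 20.2 |

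Overstatement with week 24: 55.5 − 52.7 = 2.8 and 33.5 − 30.5 = 3.0 points. With week 18: 64.3 − 52.7 = 11.6 and 44.1 − 30.5 = 13.6 points. These are upper limits, because they suppose that every event is found only at a scheduled scan.

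The 20.2 applies with 21-day cycles in both arms. The documents do not give the split between topotecan options. At the other extreme, with all topotecan subjects on 28-day cycles and the grid taken literally, the difference would read 64.3 − 33.5 = 30.8 points.

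**Subjects dated differently, weeks 18 to 36.** Take 66 per arm, 21-day cycles, full follow-up, and 12-weekly scans counted from week 18 (grid scans at weeks 18, 30 and 42).

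- Weeks 18–24: 66 × (0.643 − 0.555) = 5.8 and 66 × (0.441 − 0.335) = 7.0. Dated week 24 by the text and week 30 by the grid.
- Weeks 24–30: 66 × (0.555 − 0.479) = 5.0 and 66 × (0.335 − 0.255) = 5.3. Dated week 30 by both.
- Weeks 30–36: 66 × (0.479 − 0.414) = 4.3 and 66 × (0.255 − 0.194) = 4.0. Dated week 36 by the text and week 42 by the grid.

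Dated differently: 5.8 + 7.0 + 4.3 + 4.0 = 21.1 subjects, each by 6 weeks.

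**Power.** With both arms on the same schedule, simulated log-rank power was 89.6% under either schedule. A repeat of 3,000 trials analysed at the 110th event gave 88.8% (text) and 87.9% (grid), a gap of 0.9 points with a standard error of about 0.8.

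**The case against.** The strongest reply is that the plan states the rule plainly, twice, in calendar weeks. Under that rule a week-24 scan precedes 6 months and nothing is lost. The grid's scan marks point to footnotes that are not supplied and may repeat the calendar schedule. This stands: the grid cannot be taken as proof that the scans were left out of the plan. It does not remove the conflict, because the unmarked column has no scan mark for a footnote to qualify.

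A reader might infer more than the documents support:

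- That 6-month PFS will rest on week-18 status. This needs sites to follow the bare grid over explicit text. It also fails for 28-day topotecan, where Cycle 7 is week 24. Deaths and End of Treatment scans between weeks 18 and 26 would count in any case.
- That subjects who stop drug without progression move to 12-weekly scans. That depends on footnote 13, which is not supplied.
- That all 31 or so subjects expected to progress in weeks 18 to 36 are affected. With 12-weekly scans counted from week 18, about 10 of them are dated identically. All 31 would differ only under another start, such as a first 12-weekly scan at week 48, and the documents do not state one.
- That the late-scan column in the original protocol's table proves an error. That table is superseded and is background only.

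The bias in the 6-month rate is also largely common to both arms when both are on 21-day cycles, and the Amendment 3 Statistical Methods text gives no test or alpha for that rate.

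**Conclusion.** The point holds as a conflict between table and text within Amendment 3, and it should be reconciled. It is not a proven absence of scans and does not undermine the sample size. The overstatement of 6-month PFS is an upper limit of about 12 and 14 points, against about 3 under the text. It is conditional on the grid being followed, 21-day cycles, exponential PFS at the plan's medians, and detection only at scheduled scans. On that footing the arm difference and the log-rank power barely move.

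The more practical risk is inconsistent dating: about 21 of 132 subjects if sites divide between the two readings, given the assumed week-18 start. A literal cycle reading would also put 28-day topotecan on a different scan clock. The small effect on the arm difference cannot be assumed there.

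**What to change.** Reconcile Appendix A with the synopsis text. Show the tumor-assessment row in calendar weeks from Cycle 1-Day 1 (6, 12, 18, 24, 30 and 36, then every 12 weeks until progression) for both arms, whatever the cycle length. Replace the scan marks under Cycles 3, 5 and 7 accordingly, and state the week from which the 12-weekly interval runs. Check that footnotes 4, 8 and 13 agree with this.

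The cost is one table correction in an amendment. It adds no scan, because the text already requires all of them.
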